HBB Prompt will be an interactive tool that guides frontline providers through the steps needed to save newborn babies at birth. HBB Prompt will facilitate individual and group training in health facilities using the Low Dose High Frequency model (LDHF) for resuscitation skills retention. Our group has successfully developed and tested a related application for the Neonatal Resuscitation Program (NRP), the newborn stabilization algorithm used in North America.(8) We will use lessons learned from our previous work to robustly develop HBB Prompt by integrating human factors and user-centered design approaches. We will engage end-users and HBB Master Trainers to iteratively collect feedback to develop HBB Prompt for both individual and small group resuscitation practice. Our iterative approach will mitigate the common scenario of mobile health (mHealth) solutions unable to achieve sustained success at scale due to lack of comprehensive input from frontline users. We will pilot the app at a single centre and compare it to a control site for HBB skills retention.

Hypothesis: Applying a user-centered design approach of collecting iterative qualitative data from end-users regarding learning needs and facilitators and barriers to HBB skills maintenance will enable creation of a mobile app that will improve skills retention in an intervention group versus a control group.

Objectives

1. To develop a refined HBB Prompt app through user-centered design involving input from frontline birth attendants in Uganda.
2. To train a minimum of twenty health workers from two district hospitals in Southwestern Ugandan in HBB 2.0 and Essential Care for Every Baby within 6 months of the start of the project.
3. To determine the impact of the HBB Prompt app on HBB skills retention of providers in the intervention site compared with providers in the control site (higher average OSCE B test scores) 12 months after training.

Objective 1: To develop a refined HBB Prompt app through user-centered design involving input from frontline birth attendants in Uganda.

Phase 1a

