We will train a minimum of 20 frontline health providers (10 per hospital) from two district hospitals in southwestern Ugandan in HBB 2.0 and ECEB. HBB and ECEB training will be conducted by national trainers in the ratio of 1 trainer to 6 providers. Providers will undergo ECEB training in addition to HBB as these training programs are recommended by the Uganda Ministry of Health to be offered together.

HBB 2.0 training takes place over one day and ECEB training over two days. Participants will be invited from both hospitals to any one episode of training to minimize the number of frontline birth attendants in trainings at any single time.

One hospital will be randomly selected and its providers will have access to the most updated version of HBB Prompt (beta) at the end of the trainings (Intervention arm). The control group will not have exposure to the HBB Prompt app post training.

Participants in both centers will be asked to achieve a minimum practice target of once per day. Our recommended frequency to use the app will be once per shift (i.e. run through 1 simulation per person as a pair). An HBB article from earlier this year showed the greatest improvement when health workers practiced at the beginning of every shift. As it may be difficult to ensure that it is done at the beginning of shift, we will leave the timing of once a shift practice at the discretion of providers. Whenever a new team comes on, they will be recommended to ask the previous team if they did a simulation practice. If not, then they will remind the outgoing team to complete it. These recommendations on frequency of practice will be offered at both the intervention and control sites. All sites will receive resuscitation practice mannequins and a resuscitation practice table.

We will present to the Health Facility team the results of their HBB simulation practice frequency as captured by the HBB Prompt app analytics in the intervention arm. This app analytics data on frequency of practice will be presented to the health facility every two months during the one year study period. The app will be designed to generate both individual and group (facility) practice frequency. Both intervention and control arms will have a standard log-book to record frequency of practice. The accuracy of the log-book will be compared to the data retrieved from app analytics in the intervention arm.

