Objective 3: To determine the impact of the HBB Prompt app on HBB skills retention of providers in the intervention site compared with providers in the control site.

1. Primary outcome: comparison of OSCE B scores in intervention (HBB Prompt) vs. control group. (17 out of 23 constitutes a pass score)
 - a. At 0 months, (immediately before and after training)
 - b. At 3 months
 - c. At 6 months (midline)
 - d. And at 12 months (endline)
2. Measures during the 12-month period of intervention in HBB Prompt site and control site at two unannounced visits (4 months, 9 months):
 - i. HBB 2.0 Knowledge check (18 questions)
 - ii. Bag and mask ventilation skills check (score out of 14)
 - iii. OSCE A (score out of 12, 9 out of 12 constitutes pass score)
 - iv. In addition to the OSCE skills checklist as scored by raters, we will use the Augmented Infant Resuscitator (AIR) to objectively measure quality of newborn resuscitation during every ventilation epoch. AIR records time stamped data on ventilation quality, such as presence of air leak or obstruction and ventilation rate (www.air-device.com).
 - b. Data on potential confounders will be collected for each site (volume of deliveries, workload in labor and delivery, burnout, motivation, baseline supervision, experience, previous training, provider level, number of patients/areas each provider is responsible for, length of time provider has been in practice, availability of equipment, availability of an HBB algorithm posted at the bedside.)
 - c. Other clinical outcomes will be collected from the Ministry of Health Birth Register: For each patient: date of birth, time of birth, birth weight, death before discharge, admission to nursery, 1 and 5 minute Apgar scores, resuscitation status at birth and resuscitation outcome.
 - d. Reports generated and presented to each site every 2 months: frequency of practice, number of deliveries, number of infants requiring bagging, fresh stillbirths, neonatal mortality in hospital
3. App analytics
 - a. Pattern of usage
 - i. Which components of the app are being used?
 - training mode, simulation mode, help videos, quizzes
 - b. Frequency (login, page use), purpose device ID
 - i. Is low dose high frequency happening? – Frequent, short duration access?
 - c. Self practice vs. peer or group practice
 - d. Trends for scores for simulations and quizzes

4. We will conduct exit focus group discussions and interviews at both intervention and control sites:

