Audio recordings from focus groups and interviews will be transcribed. Transcripts will be reviewed for themes using a grounded theory approach. Data analyses will take place after each iteration of phase 1b to incorporate feedback to improve and adapt each version of the HBB Prompt prototype. At least two investigators will independently read all transcripts at least twice to obtain an overall understanding, identify data codes and ensure that all comments are carefully considered and included. Categories within the themes will then be identified, and any relationships among themes determined. As data are entered into the analyses, categories will continue to be generated, until there is no new data that cannot be categorized under existing codes. When this occurs, it is likely that a range of functions and features of an ideal mobile app as a learning tool for HBB will have been categorized. Further, we will also likely have categorized an assortment of barriers and facilitators to skills maintenance and implementation of HBB Prompt. A similar analytic approach has previously been successfully used in the development of an osteoporosis clinical decision support tool (10).

Phase 2

Comparison of intervention versus control for the following outcomes will be analyzed at each time point using the Mann-Whitney U test:

- Primary outcome: OSCE B score at 12 months
- Secondary outcomes:
 - OSCE B scores at 0, 3, and 6 months
 - At two unannounced site visits (months 4 and 9)
 - Knowledge check score
 - BMV skills check score
 - AIR data
 - Percentage of time with correct ventilation rate
 - Percentage of time with air leak during ventilation
 - Percentage of time with obstructed airway during ventilation
 - Time to effective ventilation
 - OSCE A score

Additionally, comparison of OSCE B score after training at 0 months and at 12 months within each arm using the Wilcoxon-signed rank test

	0 months	3 months	4 months	6 months	9 months	12 months
OSCE B	Pre/post HBB training	x		x		x
OSCE A			x		x	
Knowledge check			x		x	
Bag-mask skills			x		x	
AIR			x		x	

Descriptive statistics compared between intervention and control for:

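### Change in OSCE B from post-training to month 12 is tested only within each arm, so these tests cannot show that retention differs between the two hospitals

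*Protocol*

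**What the plan says.** Objective 3 asks about the "impact of the HBB Prompt app on HBB skills retention of providers in the intervention site compared with providers in the control site". In the Objectives list this is tied to an expected result at a single time point, "higher average OSCE B test scores) 12 months after training".

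In Data Analysis, Phase 2, the main analysis is between arms: "Comparison of intervention versus control for the following outcomes will be analyzed at each time point using the Mann-Whitney U test". The first item under it is "Primary outcome: OSCE B score at 12 months"; OSCE B at 0, 3 and 6 months is secondary. Each of these tests uses the score at one visit.

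The same section then adds a "comparison of OSCE B score after training at 0 months and at 12 months within each arm using the Wilcoxon-signed rank test". No other planned analysis uses the change from post-training to month 12, and no between-arm analysis of that change is given.

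Objective 2, Phase 2a, sets a minimum of 20 trained providers, 10 per hospital, and no maximum. Under Objective 3, OSCE B is marked out of 23 ("17 out of 23 constitutes a pass score"). The Protocol gives no alpha, expected decline, SD of change or expected dropout.

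**The concern.** Retention is about what providers keep of the skill they had after training. The Protocol collects the scores needed to measure this, but analyses the loss only inside each hospital. Significance in one arm and not in the other does not test whether the arms differ. It can arise from chance alone when both arms lose the same amount.

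Two features make this pair of tests easy to misread. First, the welcome result in the app arm is a non-significant one, and with about 10 providers a p-value above 0.05 is compatible with a real loss of skill. Second, the power of a within-arm test depends on the number assessed, so the arm with fewer providers is less likely to show a significant decline whatever the app does. Only a minimum per hospital is set, so arm sizes may differ.

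The 12-month Mann-Whitney test does not fill this gap. It compares where providers end, without regard to where each one started after training.

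**Working it through.** The Protocol gives no power, effect size or alpha, so there is no stated figure to reproduce. The check asks how often the two within-arm tests disagree when the true decline is the same in both arms.

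**Inputs from the Protocol:** one signed-rank test per arm (Data Analysis, Phase 2) and at least 10 providers per arm (Objective 2, Phase 2a).

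**Assumptions, not in the Protocol:** two-sided 5% level; normally distributed change with SD 3 points; true decline of 1 to 4 points, equal in both arms; independent providers. Seven assessed providers is used to illustrate an arm that falls below 10.

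**Step 1, power of one within-arm test.** The exact signed-rank test with n = 10 rejects when the smaller rank sum is at most 8 (exact size 0.0488). Simulated power p at a 2-point decline is 0.30 for n = 7, 0.45 for n = 10 and 0.65 for n = 15.

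**Step 2, control significant and app arm not, 10 v 10.** The arms are independent, so the probability is p × (1 − p):

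| Equal decline (points) | p, n = 10 | p × (1 − p) |
|---|---|---|
| 1 | 0.15 | 0.13 |
| 2 | 0.45 | 0.25 |
| 3 | 0.78 | 0.17 |
| 4 | 0.95 | 0.04 |

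The reverse pattern has the same probability. At 2 points, exactly one arm is significant in 2 × 0.45 × 0.55 = 0.50 of trials. The 25% is the maximum, since p × (1 − p) cannot exceed 0.25.

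**Step 3, unequal arms, 2-point decline.**
- 7 app v 10 control: 0.45 × (1 − 0.30) = 0.32.
- 10 app v 7 control: 0.30 × (1 − 0.45) = 0.165, about 16% with unrounded powers.

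The smaller arm is favoured, whichever it is.

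**Step 4, integer scores.** Scores were rounded and capped at 23, with an assumed post-training mean of 20, SD 2.5 and correlation 0.5 between visits (4,000 trials, 10 per arm). Equal losses of 1, 2 and 3 points give the control-only pattern in 13.5%, 24.3% and 10.8% of trials. It occurs together with a non-significant 12-month Mann-Whitney test in 12.6%, 23.2% and 10.4%.

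**Step 5, one between-arm test instead.** A Mann-Whitney test on individual change scores, 10 per arm, with equal loss, is significant in about 4.3% of trials (4.2% to 4.5% over the losses tried). About half of these favour the app.

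**The case against.** The strongest reply is that the Protocol already answers Objective 3 between arms. The 12-month OSCE B comparison is primary, Objective 3 itself refers to higher 12-month scores, and the signed-rank tests are only additional. This stands. A reader might infer that the arms are never compared, or that the retention conclusion would rest on the two paired tests. The document supports neither. It nowhere says that an app effect will be concluded because one arm is significant and the other is not. Asking whether skills fell within each hospital is also a legitimate descriptive question.

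It can be added that the primary test would usually be null when the misleading pattern appears: at an equal 2-point loss, in 23.2 / 24.3 = 95% of such trials. That is true and limits the harm. But a null primary result in a small study is also when supporting results attract attention, and the Protocol offers nothing else that compares the loss.

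A reader might also infer a built-in bias toward the app. That does not follow. With equal arms both patterns are equally likely, and nothing in the Protocol suggests that the app arm will be the smaller one.

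Finally, a SAP may settle points of reporting. The two within-arm tests, however, are a method that the Protocol itself fixes.

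**Conclusion.** The point holds as a weakness of the supporting retention analysis; the primary test is unaffected. The two within-arm tests cannot show that retention differs between the hospitals, and a non-significant result in about 10 providers does not show that skill was kept.

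Under equal true decline and 10 per arm, the chance that control alone appears to decline is 25% at most and 4% to 25% over declines of 1 to 4 points. At a 2-point decline it moves to about 32% or 16% when 7 providers in one arm are compared with 10 in the other. These percentages rest on the assumed SD, decline, alpha and independence of providers. The logical point does not depend on them.

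This does not mean that a contrast of change should displace the 12-month score as the primary outcome. The Protocol chose that outcome, and the change analysis belongs beside it.

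**What to change.** In Data Analysis, Phase 2:

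1. Keep the between-arm comparison of the 12-month OSCE B score as primary.
2. Replace the two within-arm p-values with each arm's change from post-training to month 12, as an estimate with a 95% CI, labelled descriptive.
3. Add one supporting between-arm comparison that uses the post-training score, either the difference in change or the 12-month score adjusted for the post-training score, with a 95% CI.
4. State that no app effect on retention will be inferred from one arm being significant and the other not.
5. State that, with one hospital per arm, a provider-level interval cannot separate the effect of the app from that of the hospital.

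The cost is a few sentences and two lost p-values. No new data are needed, because the visit schedule already has OSCE B after training and at 12 months. The limit in item 5 remains: the added comparison removes an avoidable source of error but does not cure the two-hospital design.

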Birth asphyxia causes up to 1.8 million newborn deaths and stillbirths every year. This global tragedy can be prevented by effectively Helping Babies Breathe at the time of birth. Helping Babies Breathe (HBB) (Appendix 1) is a newborn stabilization course that has been shown to reduce early neonatal mortality by up to 47% in Tanzania.(1) Significant reduction in intrapartum still births and first day mortality have also been demonstrated in other low and middle-income countries. (2, 3) The knowledge and skills acquired in this course, however, have been shown to rapidly deteriorate over time, with skills deteriorating more than knowledge. (4) The largest systematic review on this topic suggests that although not commonly included in resuscitation programs, refresher training is likely necessary to improve the impact on neonatal mortality.(5) Mduma et al have demonstrated that frequent brief on-site simulation with the HBB program can have a sustained impact on mortality.(6) Furthermore, regular, low intensity, manikin-based skills training with peers has been shown to allow workers to maintain bag mask ventilation skills at one year. (7) We propose to improve sustainability of HBB's impact by increasing skills retention with an innovative mobile application called HBB Prompt. If successful, our application provides a novel, low-cost method for providers to receive regular simulation training with peers.

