- Demographic data and potential confounders (volume of deliveries, workload in labor and delivery, burnout, motivation, baseline supervision, experience, previous training, provider level, number of patients/areas each provider is responsible for, length of time provider has been in practice, availability of equipment, availability of an HBB algorithm posted at the bedside)
- Other clinical outcomes: death before discharge, admissions to the nursery, number of deliveries, number of infants requiring bagging, fresh stillbirths, neonatal mortality prior to discharge
- Frequency of practice, self vs. group practice, skills practiced

Qualitative data from focus groups and interviews:

- Similar to in phase 1, audio recordings will be transcribed and reviewed using a grounded theory approach. Coded themes and categories will be compared descriptively between participants in the intervention versus the control groups.

Budget Summary

Budget category	Total CAD
Remuneration - funding recipient's employees	35,441
Fees - Subcontractors	19,642
Reimbursable Travel Costs	9,960
Reimbursable Goods and Supplies	9,304
Reimbursable Equipment Costs	2,640
Reimbursable Project Administration Costs	2,845
Sub-grants	20,000
Total Project in CAD	99,831

References

1. Msemo G1, Massawe A, Mmbando D, Rusibamayila N, Manji K, Kidanto HL, Mwizamuholya D, Ringia P, Ersdal HL, Perlman J. Newborn mortality and fresh stillbirth rates in Tanzania after helping babies breathe training. *Pediatrics*. 2013 Feb;131(2):e353-60. doi: 10.1542/peds.2012-1795. Epub 2013 Jan 21.
2. Kc A1, Wrammert J2, Clark RB3, Ewald U2, Vitrakoti R4, Chaudhary P4, Pun A2, Raaijmakers H2, Målqvist M2. Reducing Perinatal Mortality in Nepal Using Helping Babies Breathe. *Pediatrics*. 2016 Jun;137(6). pii: e20150117. doi: 10.1542/peds.2015-0117.
3. Goudar SS1, Somannavar MS, Clark R, Lockyer JM, Revankar AP, Fidler HM, Sloan NL, Niermeyer S, Keenan WJ, Singhal N. Stillbirth and newborn mortality in India after helping babies breathe training. *Pediatrics*. 2013 Feb;131(2):e344-52. doi: 10.1542/peds.2012-2112. Epub 2013 Jan 21.

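### Minor, free improvement: in-hospital death and nursery admission are compared crude between the two hospitals, although birth weight is already extracted for every baby and could be used to band and standardise them

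*Protocol*

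**What the plan says.** Data Analysis, Phase 2 assigns Mann-Whitney tests to OSCE B at 12 months (primary) and to a list of secondary skill and knowledge measures. No clinical outcome is in that list. Under a separate line, "Descriptive statistics compared between intervention and control for", it places the other clinical outcomes: "death before discharge, admissions to the nursery, number of deliveries, number of infants requiring bagging, fresh stillbirths, neonatal mortality prior to discharge".

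The source is the Ministry of Health Birth Register (Objective 3, item 2c), with these fields: "For each patient: date of birth, time of birth, birth weight, death before discharge, admission to nursery, 1 and 5 minute Apgar scores", followed by resuscitation status and outcome. Age or time at death and date of discharge are not listed. Item 2d adds two-monthly reports to each site that include in-hospital neonatal mortality.

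On confounding, item 2b says "Data on potential confounders will be collected for each site". The list that follows covers delivery volume, workload, staff experience, supervision, equipment and similar. It contains nothing on the babies themselves.

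On the timing of benefit, the opening background paragraph describes HBB as "shown to reduce early neonatal mortality by up to 47% in Tanzania". It then adds: "Significant reduction in intrapartum still births and first day mortality have also been demonstrated in other low and middle-income countries".

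The Randomization section allocates the app to one of two named hospitals by a single random number.

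**The concern.** Birth weight is a baseline characteristic of the baby, and it plausibly drives both death and nursery admission. The plan collects it and gives it no stated role. With two hospitals, one draw decides which gets the app, so randomisation cannot balance case mix. If one hospital delivers more small babies, its crude death and admission figures will be higher whatever the app does. A reader of the results table, or of the two-monthly reports, has no means of seeing this.

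There are two smaller matters. The first and last items in the outcome list appear to name the same thing, death in hospital before discharge, and nothing distinguishes them. Also, a count that ends at discharge has no fixed window, and without age at death the first-day figure that the background cites cannot be derived. Resuscitation outcome might capture deaths during resuscitation, but not the rest of the first day.

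What is at stake is how a descriptive table is read, not the trial's main conclusion.

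**Working it through.** The protocol gives no event rate, small-baby share, length of stay or number of births for either hospital, so it has no figure to reproduce. Every input below is an assumption, chosen to show how large the effect could be.

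**1. Case mix with no app effect**

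Crude rate = (share small × risk in small) + (share other × risk in other). Weight-specific risks are the same in both hospitals: 80 per 1,000 in small babies (below 2,500 g) and 10 per 1,000 in the others.

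- 10% small: 0.10 × 80 + 0.90 × 10 = 17.0 per 1,000
- 15% small: 0.15 × 80 + 0.85 × 10 = 20.5 per 1,000; ratio 20.5 / 17.0 = 1.21
- 20% small: 0.20 × 80 + 0.80 × 10 = 24.0 per 1,000; ratio 24.0 / 17.0 = 1.41

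Standardising removes this part. Take the 10% v 15% case with equal births, so that 12.5% of all babies are small. Both hospitals then have 0.125 × 80 + 0.875 × 10 = 18.75 per 1,000, a ratio of 1.00.

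**2. Range over other assumptions**

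Here the app hospital is taken to have fewer small babies, and the ratio is app over control.

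- Mildest case (risks 60 and 10 per 1,000, shares 10% v 12%): 15.0 / 16.0 = 0.94
- Strongest case (risks 100 and 8 per 1,000, shares 8% v 16%): 15.36 / 22.72 = 0.68

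Each would look like a benefit. With the hospitals swapped, each would look like a harm. The same mechanism applies to nursery admission, for which no figures were assumed.

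**3. Why age at death is worth having**

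- Equal first-day mortality of 10 per 1,000, with later in-hospital deaths of 3 v 8 per 1,000: (10 + 8) / (10 + 3) = 18 / 13 = 1.38
- A true 30% first-day reduction (7 v 10), with 5 later deaths per 1,000 in each hospital: 1 − (7 + 5) / (10 + 5) = 1 − 12 / 15 = 20%
- Length of stay alone: let a share s of 7-day deaths fall on day 1 and the rest spread evenly over days 2 to 7. A stay of d days captures s + (1 − s)(d − 1)/6. With s = 0.4 and stays of 1 v 3 days, 0.40 / 0.60 = 0.67. With s = 0.7 and stays of 2 v 3 days, 0.75 / 0.80 = 0.94. Deaths counted over a fixed 24 hours would give 1.00 in both.

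**The case against.** The strongest reply is that nothing here is inferential. Objective 3 concerns skills retention measured by OSCE B, and the clinical outcomes are outside the primary and secondary lists. The plan calls the comparison descriptive and states no test or claim about mortality. Birth-weight bands are also ordinary content for a statistical analysis plan, the field is collected, and nothing forbids its use. This stands, and it is why the point is an improvement and not an error. It answers less for age at death: a later analysis plan cannot use a field that was never extracted.

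Further objections also stand in part:

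- Every magnitude is assumed. The documents give no sign that the two hospitals differ by any of the amounts used.
- The duplicate label probably comes from merging the per-baby items (2c) with the report items (2d). It is clerical and biases nothing.
- The source is a ministry register, and the documents do not say that it holds age or time at death.
- Standardising for birth weight leaves every other hospital difference in place, and banding thins what may be few events.

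A reader might infer that the death outcome should be replaced by death within 24 hours because HBB acts on day one. The background does not support that, since it cites early neonatal mortality as well as first-day mortality. A replacement would discard deaths that the rationale counts. The intrapartum part is already covered by fresh stillbirths, which are listed separately and do not depend on length of stay after birth. A reader might also suspect bias from babies transferred out, but the protocol does not mention transfers, so this is only a possibility.

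**Conclusion.** The point holds as a minor, free improvement. Death and nursery admission are set out for a crude comparison between one hospital per arm, while a baseline variable that could remove one obvious source of imbalance is collected and left without a role. Under the assumed risks of 80 and 10 per 1,000, a modest difference in small-baby share (10% v 15%) produces a ratio of 1.21 with no true effect. Over the other assumptions tried, the ratio of the lower to the higher rate runs from 0.68 to 0.94. These show what is possible, not what is likely at these two hospitals.

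It would be tempting to conclude that the trial's findings are compromised, or that the plan presents a mortality difference as an app effect. Neither follows. The OSCE B result is unaffected, and the plan makes no mortality claim. Nor would standardisation turn the comparison into an estimate of the app's effect, because the remaining hospital differences cannot be separated from the app.

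**What to change.** 1. Report in-hospital death and nursery admission per birth within birth-weight bands for each hospital. Two bands (below 2,500 g, and 2,500 g or more) may be enough if events are few. Add one birth-weight-standardised rate per hospital, using the pooled birth-weight distribution of both hospitals as the standard. This needs no new data.
2. State beside the table that the comparison is descriptive, because other differences between the two hospitals cannot be separated from the app. This costs one sentence.
3. Merge the two overlapping death labels into one in-hospital death outcome, use that name throughout, and keep the outcome. This is an editorial change.
4. Where the birth register or ward record already holds it, also extract age at death, or whether the baby died within 24 hours. Show first-day death next to in-hospital death, not in its place. This adds one field to the extraction and has to be decided before extraction starts. If the records do not hold it, say so and leave it out.

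### Does the control hospital have a source for the planned description of self versus group practice and of skills practised?

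*Protocol*

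**What the plan says.** The Phase 2 part of Data Analysis has a list headed "Descriptive statistics compared between intervention and control for". Its practice entry reads "Frequency of practice, self vs. group practice, skills practiced".

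The statements on how practice is recorded are in two other places:

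- **Objective 2, Phase 2a.** The shared record is described in one sentence: "Both intervention and control arms will have a standard log-book to record frequency of practice". On access to the app: "The control group will not have exposure to the HBB Prompt app post training". The two records are checked against each other at the intervention hospital only: "The accuracy of the log-book will be compared to the data retrieved from app analytics in the intervention arm".
- **Objective 3, item 3 (App analytics).** Item 3c is "Self practice vs. peer or group practice". Item 3a asks which parts of the app are used and gives its training and simulation modes, videos and quizzes as the categories.

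**The concern.** The analysis section promises a two-arm description of three practice measures, while the data-collection sections clearly supply only one of them in both arms. Self versus group practice appears as a collected item only in the app data. Skills practised is not itemised anywhere, and the nearest entry, use of app components, concerns modules of the software and not resuscitation skills.

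This could matter because the trial compares two hospitals. If OSCE B scores differ at 12 months, a reader will want to know whether control staff practised alone or with colleagues, and what they practised. Practice details are recorded as they happen. If the control hospital does not note them during the 12 months, no later analysis plan can restore them.

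**Working it through.** No arithmetic applies: the protocol gives no figure that bears on this point. The check is to trace each measure in the practice bullet, arm by arm, through everything the protocol says is collected.

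| Measure | Intervention hospital | Control hospital |
|---|---|---|
| Frequency of practice | Log-book and app analytics | Log-book |
| Self versus group practice | App analytics, item 3c | None stated |
| Skills practised | None stated exactly; app components (item 3a) are a proxy | None stated |

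Other places that might supply the missing entries were then read:

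- **Two-monthly site reports (Objective 3, item 2d).** Frequency is the only practice variable.
- **Unannounced visits at 4 and 9 months (Objective 3, item 2).** These measure knowledge and performance, not what staff have been practising.
- **Exit discussions and interviews (Objective 3, item 4).** The control-site topics are barriers, facilitators and ideas for keeping skills up. The topics for both sites are workload, burnout, motivation, supervision, patient load and equipment. Neither measure is listed.
- **App output by person and by facility (Phase 2a).** This is a level of reporting, not solo versus peer practice, and it exists only where the app does.

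So the tracing holds: no control-arm source is stated for two of the three measures. What follows from that depends on three further readings.

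1. **Is the log-book sentence a closed list?** "Both intervention and control arms will have a standard log-book to record frequency of practice" gives a purpose. It does not set out the columns or say that nothing else is entered. No sentence says the control hospital will not record type of practice or skill. There is therefore no contradiction between the analysis list and the log-book description.

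2. **Does the text point to a source?** The three measures share one bullet under a heading for both arms, and the first comes from the log-book. Who practised with whom, and what was practised, are ordinary companion entries in a practice log. Since app modules are not skills, skills practised was probably not meant to come from the app. This is inference, but it is the natural reading.

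3. **Does the recommended practice make pairing a control-site measure?** Phase 2a describes practice as "run through 1 simulation per person as a pair", but that phrase explains how often the app should be used. What is extended to both hospitals is narrower: "These recommendations on frequency of practice will be offered at both the intervention and control sites". The text does not clearly recommend pairing at the control site, so this adds little to the case for a change.

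Last, the use of the measures. The Mann-Whitney comparisons cover OSCE B, OSCE A, the knowledge check, bag-mask skills and the AIR measures. The Wilcoxon signed-rank test covers OSCE B within each arm. Neither practice item enters any of them.

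**The case for a change.** The best case for a change is that this is a matter of collection, which a statistical analysis plan cannot repair. The protocol itself commits to a comparison in both arms, yet names collection of one measure only through a tool the control hospital lacks, and does not name collection of the other at all. The app is meant to support both individual and group training, so how control staff practise is useful context for any difference between two hospitals. A sentence in the protocol and extra log-book columns would probably cost little, and would have to be in place before Phase 2 recording begins.

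Much of this stands: the sources are not stated, and data not recorded would be lost. What does not stand is the step from not stated to not recorded. The columns of a log-book are form-level detail that a short protocol commonly leaves to the form, and the form is not shown. Elsewhere, too, this protocol names variables without an instrument: burnout and motivation are to be collected, with no scale given. Asking for more here is a preference for completeness. It does not identify something the protocol states wrongly.

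**Conclusion.** The observation is accurate, but no change to the plan follows. It is a gap that those who draw up the log-book would fill sensibly from the analysis list itself.

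Its size is part of one descriptive bullet. Two of three practice measures lack a stated control-arm source. A count of unstated sources says nothing about bias or precision, and the primary result, the secondary outcomes and all planned tests would be the same with or without these items.

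The conclusion assumes that the log-book is laid out with the analysis list in view before Phase 2 recording starts. If it turned out to hold frequency alone, self versus group practice could still be described at the intervention hospital from app analytics. Skills practised would be limited to the app-component proxy there, and the control hospital would contribute frequency only. That would thin the context for interpreting the trial but would make no planned conclusion unsound.
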